574 sedation or GA [23]. Of the 25 children, 17 (68%) had incomplete stable fracture patterns and six (24%)
575 had complete but minimally displaced fractures. In all, 23 (92%) children could be treated non-
576 operatively. Two children had unstable and displaced fractures and underwent surgery.

577
578 If proven safe and feasible, non-operative treatment for undisplaced and minimally displaced LHCF
579 would relieve the child of hospital admission, anesthesia and surgery and reduce parent's need for time
580 off work and reduce overall healthcare costs.

581
582 The investigators suspect a significant decrease in the need for operative management based on the
583 results of this project.

584 11 Risk analysis

585 The risks that occur in this study are associated with the general risks of non-operative treatment for
586 LHCF.

587 11.1 Treatment-related risks

588 Discomforts/risks from casting:

- 589 • Heat injury
- 590 • Pressure sores and skin breakdown
- 591 • Dermatitis
- 592 • Joint stiffness

593 11.2 Study disadvantages

594 Extra visits to the outpatient clinic. We follow all patients with seven visits to the outpatient clinic. This is
595 four more than with standard treatment and might be viewed as a disadvantage.

596 11.3 Study-related risks

597 11.3.1 Secondary displacement

598 During non-operative treatment of fractures, the risk of secondary displacement is well known. The risk
599 of secondary displacement of an initially undisplaced LHCF varies from 4% to more than 40%
600 depending on the initial stability and displacement [12]. As the initial stability in this study is evaluated by
601 MRI the investigators suspect that the risk of secondary displacement will be close to 4%.

602 **11.3.2 Radiation**

603 In comparison with the standard follow up of LHCF there are four additional visits to the out-patient clinic
604 with radiographs of the elbow in AP, ML and IO view. Collectively, the effective dosage is 0.004 mSv -
605 far below 0.1 mSv and is considered insignificant.

606 **11.3.3 Loss of privacy**

607 Patients' private and confidential medical information may get disclosed and confidentiality broken.
608

609 **11.4 Actions to minimize increased risks**

610 General treatment-related risks will be present whether the patient participates in the study or not. Such
611 risks will be managed by use of standards of treatment, i.e. casting by trained physicians and nurses.
612

613 Risk of unnoticed secondary displacement is lowered by an increased number of FUs with radiographs
614 and MRI in case of unstable injury.
615

616 The risk of loss of privacy and confidentiality will be managed by strict adherence to data safety and
617 security procedures explained elsewhere in this CIP.
618

619 The study will be implemented according to current valid international guidelines (ICH-GCP and ISO
620 14155). The ethical position is based on the Declaration of Helsinki, thus guaranteeing optimal
621 protection of patient interests.

622 **12 Informed consent process**

623 **12.1 Special considerations to consent pediatric patients**

624 In this pediatric study, the parent(s) or legal guardian(s) are informed face-to-face about the study and
625 provide informed consent using specific patient information and ICF. In any case, the child is informed
626 orally in an adequate way.
627

628 Written informed consent needs to be obtained from the parent(s) or legal guardian(s). Assent is
629 obtained from any child considered to be able to understand the basic information provided.
630

631 A member of the research team will, in an undisturbed environment, explain using a plain,
632 understandable language, movies and toys to each participant and parents the nature of the study, its
633 purpose, the procedures involved, the expected duration, the potential risks and benefits and any
634 discomfort it may entail.
635

636 Parents and children will be informed that the participation in the study is completely voluntary and that
637 they may withdraw from the study at any time and that withdrawal of consent will not affect subsequent
638 medical assistance and treatment.
639

640 The participant's parents will be informed that their child's medical records will be examined directly by
641 authorized individuals involved in the study.
642

643 Consent will be obtained from every patient's parents before any study-specific procedures or
644 assessments take place.
645

646 Parents will be provided specific information and ICF describing the study and providing sufficient
647 information for the parents to make an informed decision about their child's participation in the study
648 together with general information about participating in a research project from the Danish National
649 Committee on Health Research Ethics.

650
651 Parents will in most cases have at least 24 hours to consider enrollment however, there might be factors
652 (e.g. late presentation to the ED) that dictate more emergent treatment requiring consent with less
653 consideration time.

654
655 The parents will signify their willingness to let their child participate in the study by signing and dating a
656 personal copy of the approved ICF. The consent form must also be signed and dated by a member of
657 the research team and it will be retained as part of the study records. The investigator will keep the
658 original ICF in the ISF and provide the patient's parents with a copy.

659 **13 Adverse event reporting**

660 In this clinical investigation no medical devices are used and based on the risk analyses, AEs or serious
661 AEs (SAEs) according to ISO 14155 are not collected.

662 **14 Data management**

663 This project complies with the EU's General Data Protection Regulation (GDPR) according to the
664 Danish law on data protection *Databeskyttelsesloven* and *Databeskyttelsesforordningen*.

665
666 In order to plan and conduct visits we ask that consent is given to access the patient's EHR. We ask
667 permission to retrieve patient-related data and to read entries regarding visits. We ask permission to
668 access radiographs and MRIs. We ask that access the patient's EHR is given until the conclusion of the
669 project. No access to the patient's EHR regarding the study is made before informed consent to
670 participate is given.

671
672 Consent gives the person responsible for the trial and the relevant authorities direct access to obtain
673 information in the patient's medical records for the purpose of carrying out the project as well as for
674 control purposes.

675 **14.1 Data collection, source data, storage and archiving**

676 Data management will be performed by the PI. Data handling and protection are conducted according to
677 the ISO 14155 guidelines and ICH-GCP and applicable regulations.

678
679 The eCRF collects data from each participant. Specifically all data on each patient participating in the
680 study are documented in the eCRF. The eCRF contains data items as specified in this CIP. Modification
681 of the eCRF will be made only if deemed necessary and in accordance with any amendment to the CIP.

682
683 The patient's hospital records are stored securely in the hospital's EHR (Epic Systems Corporation,
684 Verona, Wisconsin, USA).

685 **14.1.1 Electronic CRF**

686 For this study, an eCRF is designed to accommodate the specific features of the study design. Access
687 to the eCRF is password protected. The project's eCRF is stored securely using Research Electronic
688 Data Capture (RedCAP, Vanderbilt University, USA). The eCRF is to be completed in a timely manner
689 after a patient's visit (i.e. 14 days after occurrence of a documentable event).

690 **14.2 Imaging data**

691 Radiographs and MRIs are stored securely in the hospital's Picture archiving and communication
692 system (PACS).

693 **14.3 Confidentiality**

694 Privacy and confidentiality of the patient's medical data will be maintained through the study.

695
696 Fully identifiable information may be reviewed for the purpose of verifying data in the eCRF. This can be
697 carried out by the PI. Personal medical information will be treated as confidential at all times. The
698 informed consent document will contain information about the confidentiality of the medical information
699 and approval for the access.

700 **15 Regulatory affairs**

701 The CIP, associated documents, investigator's financial disclosure, the patient information and ICFs will
702 be sent to a respective EC for evaluation and approval. The relevant EC will be kept informed about the
703 study progress and events according to their specific regulations and procedures.

704 **16 Disclosures and economy**

705 The initiative for this study has been taken solely by the investigators. The investigators and affiliated
706 colleagues have not received any financial payments or other benefits from any commercial entity
707 related to the subject of this project. The investigators declare that they have no conflict of interest.

708
709 Participants do not receive any economic benefits or gifts from the participation in this project.

710
711 All expenses are paid for by the sponsor.

712 **17 Patient insurance**

713 As with any treatment in the Danish healthcare system all patients are insured and covered by The
714 Patient Compensation Association (Patienterstatningen).

715 **18 Study report and publication policy**

716 **18.1 Final Study Report**

717 The results of the statistical evaluation will be summarized in a report, which forms the basis for the
718 comprehensive FSR. The comprehensive FSR forms the basis for all future publications.

719 18.2 Publication

720 The study protocol and the trial will be registered with Clinicaltrials.gov

721

722 The results, both positive, negative and inconclusive, will be sent for submission in a peer reviewed
723 international orthopedic journal, and the results will be presented at national and international scientific
724 meetings. Reporting will adhere to the STROBE guidelines for cohort studies [31].

725 19 Termination criteria

726 The progress of the study, in particular the enrollment and safety aspects, will be closely monitored
727 together with the sponsor. The sponsor may decide to terminate the. In case of an early study
728 termination, all patients already enrolled in the study will be followed up until the last FU visit as defined
729 in the CIP.

730 19.1 Stopping rules

731 The recruitment will be put on hold for safety reason if:

732

- 733 • Secondary displacement of more than 2 mm during FU in > 75% of cases at interim analysis.

734

735 In such a case, the reported complication will be discussed with the sponsor. The sponsor will decide
736 about the actions to be taken and if the study needs to be stopped or not.

737 20 Deviations from the Clinical Investigation Plan

738 Deviations from the procedures as described in this CIP or altering the CIP without following a defined
739 process are not permitted.

740

741 A CIP deviation is any non-adherence to the protocol that does not involve the inclusion/exclusion
742 criteria, primary efficacy variable, and GCP guidelines. CIP deviations are minor and do not impact the
743 study in a major way. CIP deviations are to be reported to the sponsor within ten working days.

744

745 A CIP violation is any significant divergence from the protocol on the part of the patient, investigator,
746 sponsor, or any other responsible party that affects e.g. the inclusion/exclusion criteria, primary efficacy
747 variable, or GCP guidelines. Violations will be recorded at the study site and in the eCRF.

748 21 Amendments to the Clinical Investigation Plan

749 No changes to the approved CIP are allowed, except when the change removes immediate threats for
750 the patient safety or is of a purely administrative or logistic nature.

751

752 Should there be any need during the performance of the study to change this CIP, an amendment will
753 be developed, issued and approved by or notified to the required bodies.

754

755

756

757 22 Time schedule

Ethics Committee approvals	28.06.2021	to	01.09.2021
First patient/first visit	01.10.2021		
Last patient/first visit	01.10.2023		
Last patient/last visit	01.10.2025		
Data analysis	01.11.2025	to	01.03.2026
Final Study Report	01.03.2026	to	01.06.2026

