Secondary outcome measures	
 • Pain • Radiographic results • MRI results • Alteration in treatment regime based on MRI • Number and proportion of fractures with secondary displacement • Any early or late complications
Statistical considerations and estimated enrollment	
Sample size is estimated from previous studies which included less than 30 participants. The investigators of this study suspect that by enrolling 50 participants the age distribution and variation in fracture pattern will be representative of the background population.
 
Baseline characteristics and outcomes recorded at scheduled FU assessments will be presented using simple summary statistics.

Start of enrollment	October 2021 (estimated)
Last patient/last visit	October 2025 (estimated)
Eligibility inclusion criteria	
Inclusion criteria:
 
 • Children age 2-15 years • Diagnosis of acute LHCF (<5 days) with <5 mm of displacement on plain radiographs • Parental informed consent obtained
Eligibility exclusion criteria	
Exclusion criteria:
 
 • Contraindication(s) to performing an MRI • Unable to participate in follow-up • Existing bone pathology • Previous ipsilateral elbow fracture
Principal Coordinating Investigator	
[name] Department of Orthopedic Surgery Copenhagen University Hospital – Herlev and Gentofte Copenhagen, Denmark
 
[contact] [contact] E-Mail [contact]

Study site	
Department of Orthopedic Surgery Copenhagen University Hospital – Herlev and Gentofte Copenhagen, Denmark

Health authority	
The Danish Data Protection Agency The Danish National Committee On Health Research Ethics

Pubmed Medical Subject Heading [MeSH] terms and keywords
	
Child [MeSH] Casts, Surgical [MeSH] Fracture Fixation [MeSH] Humeral Fractures [MeSH]

Imaging review
	
All images collected will be analyzed by independent radiologists during the study

96

97

98 2 Rationale and purpose of the study

99 The treatment of LHCF is most often surgical with open reduction and fixation [1]. The diagnosis of
100 LHCF is complicated by radiographic inability to show the full extent of the injury into the unossified
101 chondral epiphysis and therefore physicians often opt for open surgical treatment. MRI; however, gives
102 a perfect view of these fractures [2–5]. This project investigates the safety and feasibility of non-

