171 Stage 1 and 2 fractures are considered stable and can be treated non-operatively. Stage 3 fractures are
 172 complete and traverse the entire course of the metaphysis, chondroepiphysis and the articular cartilage
 173 leaving the fragment without any attachment. These fractures can be undisplaced but are always
 174 considered unstable. Treatment controversy arises from the inability to distinguishing stage 1 and 2
 175 from stage 3 on plain radiographs.
 176

[figure not shown]

177
 178
 179

Figure 1 - Song classification.

180 Because of the risk of secondary displacement, operative treatment is often conducted with many
 181 surgeons choosing open reduction and fixation in all cases [19,20]. Operative fixation imposes the risk
 182 of minor complications such as superficial infection, ulcers and granulomas but also major complications
 183 such as deep infection, osteomyelitis, malunion, non-union, growth disturbance and osteonecrosis [21].
 184

185 MRI with specific cartilage sequences (figure 2) can clearly show the chondroepiphysis and studies
 186 have shown that MRI is capable of precisely showing the fracture pattern [2,3,5,22]. Using simple
 187 techniques and advances in technology to prepare the child, MRI has been shown to be feasible in
 188 younger children without sedation or anesthesia in whom this was previously thought necessary [23–
 189 30].
 190

191
 192
 193
 194

Figure 2 - MRI showing LHC. Left: Stage 1, confined to metaphysis. Center: Stage 2, fracture line stops in the chondroepiphysis. Right: Stage 3, traverses the joint cartilage.

195

196 5 Primary and secondary objectives

197 5.1 Primary objective

198

199 To describe the functional outcome two years after non-operative treatment of undisplaced and
200 minimally displaced LHCF in children.

201 5.2 Secondary objective(s)

202

- 203 • Describe the feasibility of performing a subacute MRI of the elbow in children with LHCF within 2-7
- 204 days after the injury without sedation or anesthesia
- 205 • Report MRI findings and classify fractures according to Song classification based on MRI
- 206 • Report the number and proportion of fractures that displace secondarily and their treatment
- 207 • Report final treatment; non-operative or operative
- 208 • Describe radiographic results and compare with MRI
- 209 • Report any early or late complications

210 5.3 Hypothesis

211

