257 A member of the research team will identify all eligible patients (i.e., who meet all of the inclusion and
258 none of the exclusion criteria).

259

260 The identification of eligible patients is done during the daily routine review of radiographs taken in the
261 ED of Copenhagen University Hospital - Herlev and Gentofte.

262

263 Electronic letters for FU cannot be sent to minors; therefore all parents are routinely approached by
264 phone. During this standard approach we ask permission from the EC to inquire the parents about their
265 interest and their child's eligibility in participating in this study. This inquiry will include a short
266 prescreening with questions to confirm eligibility as well as a short description of the study and
267 responsibilities for participating. None of the data of the pre-screening process will be documented
268 study specifically.

269

270 If interested in participating, the parents and the patient are invited to the outpatient clinic. Parents are
271 informed of the possibility of bringing an assessor. At the visit, a member of the research team will go
272 through the informed consent process, and explain the purpose of the study, the procedures, the
273 risk/benefits, alternatives to participation, and data protection.

274

275 For each patient participating the parents will sign and date an ICF. A copy of the signed ICF will be
276 placed into the ISF and one copy will be handed over to the parents. A more detailed description of the
277 informed consent process is provided in section 12.

278 All patients with written informed consent will be allocated to a unique patient trial number. The date of
 279 informed consent and the recruitment information is entered in the study database.

280

281 The recruitment period will be up to 24 months, during which 50 patients are planned to be enrolled.

282 **6.2 Study procedures**

283

284 The schedule of all FU visits including imaging procedures as well as the data to be collected at each
 285 visit is shown in Table 1. All FU visits with the defined time windows are calculated from the day of injury
 286 (i.e. day 0).

287

288 All participants live in the catchment area of Herlev and Gentofte Hospital within short transportation
 289 time. Information about the time and place for the follow-up examination is sent physically by mail to the
 290 current address registered in the Civil Registration System and via the electronic health record (EHR)

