 291 system. Parents are usually very keen to take their children for follow-up appointments making the risk
 292 of missing an appointment low. Any participants who miss an appointment will be contacted by phone to
 293 reschedule.

294

295 Table 1: Study schedule

296

Assessment parameters	Out-patient clinic visits and imaging procedures *										
	Visit 1**	Visit 2	Visit 3	Visit 4	Visit 5	Visit 6	Visit 7	Visit 8	Visit 9	Visit 10	
	Injury (day 0)	Screening	Information visit	Enrollment and consent	5 (± 3) days	12 (± 3) days	4 weeks	3 months	6 months	12 months	24 months
Eligibility	X										
Patient information		X									
Consent			X								
Demographics			X								
MRI				X							
If applicable - Control-MRI					(X)						
Cast removal***						X					
Radiographs and clinical exam					X	X	X	X	X	X	

297

298 * All FU visits with the defined time windows are calculated from the day of injury (i.e. day 0).

299 ** Telephone interview.

300 *** Casting may be prolonged two weeks in case of lack of callus formation at four weeks.

301

302 6.2.1 Visit 1: Screening (by phone)

- 303 • As described in section 6.1.4, the parents of potential study patients are informed about the study
304 over telephone by the PI.

305 6.2.2 Visit 2: Information visit

- 306 • All inclusion and exclusion criteria are checked to decide if the patient can participate in the study.
307 • Specific procedures for enrollment of pediatric patients are undertaken. A more detailed description
308 of the enrolment of participants and informed consent process is provided in section 6.1.4 and 10.
309 • Before any study-specific examinations are performed, the patient's parents give written informed
310 consent to participate in the study according to the CIP.

311 6.2.3 Visit 3: Enrolment, consent and preparation for MRI

- 312 • Obtain baseline demographics
313 • Book MRI
314 • Prepare child for MRI using the Child Centered Care model described in section 6.3
315 • Data verification and entry into the eCRF

316 6.2.4 Visit 4: MRI (5 (± 3) days)

- 317 • The MRI is performed according to the Child Centered Care model described in section 6.3
318 • Results of the MRI are given to the parents by phone
319 • Any necessary adjustments to the treatment plan is made
320 • Entry into the eCRF

321 6.2.5 ONLY if applicable: Control-MRI (12 (± 3) days)

- 322 • If an unstable Song stage 3 fracture is diagnosed based on the initial MRI an additional control MRI

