323 is performed during this visit
324 • Results of the MRI are given to the parents by phone
325 • Any necessary adjustments to the treatment plan is made
326 • Entry into the eCRF

327 6.2.6 Visit 5: Radiographs and clinical examination (12 (± 3) days)

- 328 • Plain radiographs of injured elbow without cast (AP, ML and IO)
329 • Clinical examination
330 – Cast condition
331 – Assessment of pain and use of pain medication
332 – Neurovascular status of the hand
333 • Entry into the eCRF

**334 6.2.7 Visit 6, 7, 8, 9 and 10: Radiographs and clinical examination (4 weeks and 3, 6, 12 and 24
335 months).**

- 336 • Plain radiographs of injured elbow without cast (AP, ML and IO)
337 • Clinical examination
338 – Assessment of pain and use of pain medication
339 – Neurovascular status of the hand
340 – Bilateral elbow assessment according to Mayo Elbow Performance Score (MEPS)
341 – Bilateral carrying angle of the elbow measured in degrees by goniometer
342 • Entry into the eCRF

343 **6.2.8 Unscheduled visits**

344 Unscheduled visits can take place at any time during the study if a need occurs or if the investigator
345 considers this to be appropriate for patient care. Information collected between study visits are to be
346 documented at the next regular study visit with the following exceptions:

- 347 • If a patient drops out of the study, a dropout form is completed at the time of dropout

348 **6.2.9 Premature study termination**

349 Patient participation in the study may end prematurely for one of the following reasons:

- 350 • Patient withdrew informed consent
- 351 • Protocol violation
- 352 • Investigator's discretion (e.g. patient noncompliance with CIP)
- 353 • Unknown/lost to FU

354

355 For each case of premature termination detailed information will be obtained explaining the
356 circumstances leading to the termination. This will be recorded on a dropout form in the eCRF.

357

358 If patients are withdrawn from the study, any collected data will be censored. Censoring allows this
359 collection of data to be accounted for in the analysis.

360 **6.3 Study treatments**

361

362 This study is not investigating any medical device. All devices in this study will be used per standard of
363 care at the participating institutions.

364 **6.3.1 Emergency treatment**

365 All patients who sustain a LHCF are initially treated in the ED with an above elbow splint. Parents and,

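### The secondary outcome on treatment altered by MRI has no recorded pre-MRI plan for each child, so averted surgery cannot be shown without an assumed or later-reconstructed reference

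*Protocol*

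**What the plan says.** The Synopsis names "Alteration in treatment regime based on MRI" among the secondary outcome measures. Section 7.2, which sets out the secondary outcomes, covers MRI results, radiographic results, secondary displacement and pain, and has no entry for this one. The closest objective in section 5.2 is "Report final treatment; non-operative or operative".

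The steps up to the first MRI are these:

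- **Emergency department (6.3.1):** "All patients who sustain a LHCF are initially treated in the ED with an above elbow splint".
- **Telephone screening (6.1.4):** "None of the data of the pre-screening process will be documented" for the study.
- **Visit 3 (6.2.3):** "Obtain baseline demographics", book the scan, prepare the child, and verify and enter data. Table 1 has no row for a treatment decision.
- **Visit 4 (6.2.4):** the MRI is done and "Any necessary adjustments to the treatment plan is made", followed by eCRF entry. The control MRI in 6.2.5 repeats this for Song stage 3 fractures.

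On data capture, section 14.1 says "The eCRF contains data items as specified in this CIP". On purpose, section 10 says "The investigators suspect a significant decrease in the need for operative management based on the" study's results.

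**The concern.** An alteration is a difference between two states, so each child needs a recorded plan before the MRI and a recorded decision after it. The second exists. For the first, the protocol documents only a splint that is the same for every child. Against a constant splint, MRI can add operations but can never be seen to remove one.

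The study has no comparison group, and part of its rationale is that MRI reduces surgery. A before-and-after contrast within each child is the most direct evidence it could offer on that. If the reference is chosen or rebuilt once results are known, the size of the effect, and even its direction, depends on that choice. An analysis plan can define a reference, but it cannot supply a pre-MRI decision that was never recorded.

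**Working it through.** The protocol gives no figure for this outcome, so there is none to reproduce. The check has two parts.

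**1. Is there a recorded reference?** The pre-MRI steps (6.1.4, Table 1, 6.2.1 to 6.2.3, 6.3.1) contain no operative or non-operative plan based on radiographs. Section 7.2.2 has the injury radiographs read and described by a senior orthopedic surgeon, but asks for no treatment decision and states neither timing nor blinding relative to the MRI. Under 6.3.4 and 14.1 the principal investigator co-reads the MRI, tells the family the treatment and manages the data. As a 2x2 table of prior plan by post-MRI decision, a splint-only prior plan leaves the operative row empty. The cell for averted surgery is then zero by construction.

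**2. How much does the reference matter?** Inputs, from the series described in section 10: 27 children, 25 completed scans, 23 then treated non-operatively and 2 operated on. Planned enrolment is 50 (6.1.4). Assumption for illustration: this cohort behaves like that series.

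Let q be the share of children who would have been planned for surgery on radiographs alone, independent of the MRI result. Among completed scans:

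- averted surgery = q × 23/25
- added surgery = (1 − q) × 2/25
- altered = averted + added

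| q | Averted | Added | Altered | Altered, of 50 |
|---|---|---|---|---|
| 0 (splint for all) | 0% | 8% | 8% | 4 |
| 0.25 | 23% | 6% | 29% | 14.5 |
| 0.50 | 46% | 4% | 50% | 25 |
| 0.75 | 69% | 2% | 71% | 35.5 |
| 1 (surgery for all) | 92% | 0% | 92% | 46 |

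Exact 95% limits (Clopper-Pearson) for the two extremes are 1% to 26% for 2/25 and 74% to 99% for 23/25.

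Section 6.3.5 also suggests surgery when the MRI cannot be completed. Counting the two failed scans in that way:

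- splint for all: (2 + 2)/27 = 4/27 = 15% (exact 95% limits 4% to 34%)
- surgery for all: 23/27 = 85% (exact 95% limits 66% to 96%)

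The same children and the same post-MRI decisions produce this whole range. Only the unrecorded prior plan differs.

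**The case against.** A literal starting state does exist: every child is splinted, and any move to surgery after the MRI can be counted. So can a change at the control MRI, because the decision after the first MRI is known. A reader might infer that the outcome cannot be measured at all; the text does not support that. This part of the objection stands, but it leaves averted surgery unmeasured.

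A reader might also infer that any reconstruction must be made in hindsight. That does not follow. Images are kept in PACS (14.2), and a reader blinded to the MRI could state a radiograph-only plan later. The protocol neither provides for this nor prevents it.

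Nor is this the only outcome bearing on the need for surgery. Section 5.2 also asks for final treatment and for radiographs to be compared with MRI. The primary objective is descriptive function at two years, and less surgery is an expectation rather than the stated hypothesis. These points stand. Still, final treatment alone can be set only against a surgery rate from outside the study.

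The 8% and 92% are extremes. Section 10 says that most, not all, of these fractures are operated on, and it speaks of the injury in general, whereas this cohort is limited to less than 5 mm of radiographic displacement. The spread shows how ambiguous the outcome is; it does not forecast an error of that size.

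Last, the eCRF and the content of Appendix 1 are not shown. Omission from section 7.2 is only supporting evidence, since complications have no entry there either.

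**Conclusion.** The concern holds for the initial MRI and for the question of averted surgery. The visible protocol specifies no radiograph-only treatment decision for each child before that scan. As written, the study can report splint-to-surgery changes and changes at the control MRI. It cannot show how often MRI averted an operation without a reference that is assumed or reconstructed later.

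The illustrative spread is 8% to 92% among completed scans, or 15% to 85% with failed scans counted as surgery, and the direction reverses between the extremes. It rests on the cited series' counts carrying over and, for the intermediate values, on the prior plan being independent of the MRI result.

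The finding itself rests on the protocol text, which confines the eCRF to items that the protocol specifies. It should be corrected because the outcome is tied to the study's rationale. The primary outcome and the sample size are not affected.

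**What to change.** - **Section 6.2.3 (Visit 3):** before the MRI, the treating surgeon enters in the eCRF the treatment intended on the AP, ML and IO radiographs alone (operative or non-operative) and the displacement in mm. The entry is dated and locked.
- **Section 7.2:** add the outcome, defined as the 2x2 table of that entry against the decision after the initial MRI, with changes reported in both directions.
- **Denominator:** all enrolled children, including those who leave the project for surgery under 6.3.5. Unusable or incomplete MRIs form a separate category, since any change there does not come from MRI findings.
- **Children already scanned:** obtain the radiograph-only plan from a reader blinded to the MRI, and label it as retrospective.

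The cost is two eCRF fields at an existing visit and a few lines of text. The main limitation is that the pre-MRI plan is hypothetical, because the surgeon knows a scan will follow. It is nevertheless free of hindsight. No treatment rule and no sample-size figure changes.
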